The RETAIN trial has been registered on clinicaltrials.gov (NCT02697799). The study profile will be regularly updated on the website and summary results uploaded to make information about the study publicly available and promote transparency.

12.Human Subjects Protection

a. Potential Study Risks

A primary risk to this study is that financial incentives either unfairly induce participants to participate in a trial that they would not otherwise participate in. This is a primary question of this trial. We will convene a data and safety monitoring board (DSMB) in conjunction with NIH to monitor any indication that this is occurring. Our hypothesis is that no population will be unfairly manipulated into participating in a trial that they would not otherwise, and that financial incentives could lead to participants examining the potential risks of a study more closely than they would have otherwise.

Supporting Research

A study led by PI [name] and Co-I [name] assessed 126 hypertensive patients' willingness to participate in RCTs of experimental antihypertensive drugs.⁷ We used a 3 x 3 within-subjects factorial design in which hypertensive patients were administered, in random sequence, 9 hypothetical RCTs which differed in their risk level (10%, 20%, or 30% chance of drug-related adverse events) and payment (\$100, \$1,000, or \$2,000 for a 10-week trial). We found that increasing payments motivated greater RCT participation, and that increasing risk levels reduced participation levels (p < 0.001 for each). Importantly, patients' participation rates declined equivalently with increasing risk levels across all payment levels studied, and the statistical interaction between risk and payment was not statistically significant (p=0.30). This shows that patients were equally sensitive to risk despite very different payment amounts, suggesting that research incentives are not undue inducements.

Furthermore, this study of payments for RCT enrollment,⁷ as well as another study by PI [name] of payments for living kidney donation,⁵¹ counter the notion that payments are unjust inducements. Specifically, in both studies, increasing payment levels were similarly motivating among patients with higher and lower incomes. Indeed, in the RCT participation study,⁷ there was an indication that larger payments may preferentially motivate wealthier people to participate (payment-by-income interaction p=0.09). The validity of these results is enhanced by the income diversity among the study samples and the substantial statistical power to identify such income-by-payment interactions if they existed.

Co-I [name] and colleagues asked participants to rate the riskiness of a new technology (transcranial magnetic stimulation) being tested in RCTs after being told they would receive \$25 or \$1,000 for trial

participation.⁸ Participants assigned to review the trials offering \$1,000 spent more time reading about study risks and other research aspects (mean = 3.7 minutes) than did patients assigned to trials offering \$25 (mean = 1.0 minutes) (p < 0.01). Larger incentives also decreased the odds that participants would skip the page of the informed consent form that described study contraindications (p < 0.05). These findings suggest that payments alert people to the possibility of risk, and encourage them to learn more about the study.⁸ Thus, rather than contravening the goals of informed consent, incentives may actually promote informed decision-making.

Another potential risk is breach of confidentiality and privacy for completion of study surveys. No identifiable data will be reported to anyone outside of the research staff. Due to the compensation in this study, we will be collecting personal information needed for completion of W-9 forms, including social security numbers, for participants receiving incentives. Accidental disclosure of social security numbers could lead to identity theft. Social security numbers will be deleted once they are no longer needed. Names and addresses will be stored in encrypted databases. These data will be viewable only by the parent trial research staff. All other researchers will be able to view only participant ID numbers. Intervention arms will be identified by code letters until both the statistician and PI agree that interim analysis is complete.

b. Potential Study Benefits

There is no direct benefit to patients for participating in the RETAIN trial. Patients may perceive the money as a benefit, but remuneration for research participation is not traditionally considered a benefit justifying human subjects research.³ Patients may benefit from participation in the parent RCTs. The RETAIN study will provide important information about the impact of incentives on enrollment and decision making, which can inform the conduct of human subjects research more generally. The participants will be debriefed about the purpose of this study and the knowledge to be gained from it.

c. Risk/Benefit Analysis

In light of the tremendous benefits to public health and individuals developing more effective programs, as well as our efforts, outlined above, to mitigate all risks associated with this study, we believe that this study presents a highly favorable risk-benefit ratio for participation.

d. Protective Measures

The first safeguard for protection of human subjects includes an experienced and well-trained study team. [name] (PI) is Associate Professor of Medicine, Epidemiology, and Medical Ethics & Health Policy at Penn, Director of the Palliative and Advanced Illness Research (PAIR Center, and Deputy Director of the Center for Health Incentives and Behavioral Economics (CHIBE) at the Leonard Davis Institute of Health Economics. He has considerable expertise in the design, ethics, and recruitment barriers of clinical trials, in leading RCTs of financial incentives to modify health behaviors, and in the

ethics of using behavioral economic approaches, including incentives, to modify health-related decisions.

i. BASC

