This modification was submitted in tandem with our colleagues on the Mobility, Outcomes, and Validated Experiences Incentive Trial (MOVE IT) study (IRB # 823491). With this change MOVE IT eligibility was assessed earlier in the enrollment process order to randomize and announce the incentives earlier to patients. We also added a note to patients randomized to the \$100 and \$300 arms that they can receive the first installment of their payment the day they decide to participate. We modified the modality of payments such that the first payment would be administered via ClinCard to ensure that all patients who enroll can go get the first installment in a non-check format. These changes were reflected in the updated debriefing and consent forms.

b. Phases II and III – Modifications to the Compared Riskiness Scale

We also updated the Compared Riskiness scale once more in an effort to counter early floor effects.

9. Approved April 23, 2018

a. Phase III – Modification to data collection and administration of surveys

In our modification approved February 21, 2018, we moved the randomization to 1 of 3 incentives to earlier in the clinical research coordinators' recruitment script to optimize the research team's ability to augment enrollment in the MOVE IT study. Patients who are randomized in this model become RETAIN subjects, and we had a way to capture demographic information on RETAIN subjects who decline participation in MOVE IT. However, we did not have a means of capturing risk perception data on patients who declined early, before reading the consent form for MOVE IT. To mitigate the issue of data missingness among these patients and to ensure we were able to execute the study successfully, we decided to include the Compared Riskiness survey in the baseline set of surveys, as well as include a minimal description of risks and benefits early in the enrollment script. This modification and change in data collection allowed us to test the interaction between incentive size and risk perception on the outcome of enrollment – and detect undue inducement, a key outcome of the study and criterion for the Data Safety and Monitoring Board to consider stopping the trial.

10. Approved January 25, 2019

a. Phase III – Addition of Qualitative Evaluation of Patient Decision-Making

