During the debriefing session, the parent trial staff will explain that all RETAIN- and parent trial-enrolled participants will receive the full high-level incentive payment (\$300 in BASC (see Section 6.d.), and \$300 in MOVE IT) in two installments. Such payment equalization is necessary because it promotes fairness by rewarding people equally for making equal contributions to the parent RCTs.

7. Randomization

a. Groups

Subjects enrolled in RETAIN will be randomized into three groups. Depending on which group they've been assigned, subjects will be presented with one of three parent trial consent forms in both electronic and paper formats (see Section 8 Study Procedures). The parent trial consent forms will display three different incentive amounts (low-, middle-, or high-level incentive). Consent 1 (low-level incentive arm) will include a paragraph on the first page that will briefly state what the study is about and indicate to patients that participation in the study is voluntary and patients will not be paid if they choose to participate. The consent form will indicate that participants will not be paid under the standard section, "Will I be paid for taking part in this study?" Consents 2 (middle-level incentive arm) and 3 (high-level incentive arm) will include a paragraph on the first page that will briefly state what the study is about and indicate that participation is voluntary and patients will be paid the incentive (middle- or high-level) incentive arm) will include a paragraph on the first page that will be paid the incentive (middle- or high-level) if they choose to participate. The consent form will also include payment information under the

standard section, "Will I be paid for taking part in this study?" that describes the level. Consents 2 and 3 will also include information regarding the impact on compensation if patients stop taking part in the study under the standard section (BASC). During debriefing, all participants enrolled in RETAIN and their respective parent trials will learn of their assignment to one of three groups.

b. Assignment

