We will implement secondary interaction analyses of risk score with incentive arm. Risk score will be treated as binary variable with 0 and >0 categories and Incentive will be treated as ordinal factor. The analysis method will be same as described in section **c**. We plan to compare the inference of this analysis with the primary approach and report accordingly.

a. Approach to outliers and influential observations

We plan to perform diagnostic checks for influential and outlier observations in interaction analyses. The analyses will be done both ways including and then excluding influential observations if any is detected. To implement the diagnostic process we will use 'car' package from R.

b. Secondary outcome measures

Attention to the informed consent document: We will assess the amount of time patients spend reading each part of the parent trial consent form by setting up each section as a "survey" in REDCap. The data extract will include the time – to the second – at which the participant moved to another section through a timestamp. The primary measure of this assessment will be time spent on the risk section; the secondary measure will be total time spent on the consent form.

Perceived risks of the research: Perceived risks of the research will be measured by a modified 9-item "compared riskiness" scale, which has been used in previous studies and refined for the RETAIN trial.

Incidence of therapeutic misconceptions: It has been hypothesized that the use of financial incentives could reduce therapeutic misconceptions, and thereby promote informed decision-making. Because patients are not accustomed to being paid for their clinical care, offering incentives could signal that research is different. We will test the hypothesized benefit of research incentives by measuring the incidence of therapeutic misconception in each incentive arm. We will assess this outcome with a 4-item therapeutic misconception tool, developed by External Advisory Board member, [name].

Understanding of the trial: To assess whether increased attention translates into improved understanding of the trial, we will use a 6-item Trial Elements Quiz, featuring core elements of the parent trials' consent forms.

Perceptions of influence or coercion: To measure general perception of coercion and voluntariness of research participation, we will use the five-item Perceived Coercion Scale of the MacArthur Admission Experience Survey.

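### Total consent-form time is compared across arms whose forms carry different payment text, so part of any longer total in the paid arms may be added text rather than attention

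*Combined protocol and SAP*

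**What the plan says.** Final SAP Section 6.b measures attention to the consent document from REDCap section timestamps. It ranks two measures: "The primary measure of this assessment will be time spent on the risk section", and "the secondary measure will be total time spent on the consent form". Section 6.c compares arms by ANOVA or the Jonckheere-Terpstra test, with incentive as an ordered variable, without covariate adjustment, among participants who consented.

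Final Protocol Section 7.a describes three forms.

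- All three have a first-page paragraph on what the study is about and on voluntariness, with a brief payment statement. On Consent 1 that statement is that "patients will not be paid if they choose to participate".
- All three have a standard payment section. For Consent 1, "The consent form will indicate that participants will not be paid under the standard section". For Consents 2 and 3, "The consent form will also include payment information under the" same section, giving the level.
- For the two paid forms only, "Consents 2 and 3 will also include information regarding the impact on compensation if patients stop taking part in the study". The protocol tags this sentence as applying to BASC.

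Final Protocol Section 8.d says that, in both parent trials, each section of the form is presented as its own REDCap survey. Nothing in the final protocol or SAP takes payment text out of the total or allows for its length.

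**The concern.** Total reading time works as an attention measure across arms only if the arms are given the same text to read. Here the randomised factor also changes the text. A patient in a paid arm who reads every shared section exactly as a $0 patient does, and who also reads the extra payment wording, has a longer total.

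Aim II (Final Protocol Section 3.a) proposes that incentives increase attention to risk information and understanding, and so improve informed consent. An upward trend in total time would be a natural thing to cite in support. The added text pushes the total in that direction, so the trend would be hard to interpret without knowing how much of it came from the payment wording.

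**Working it through.** **No figure to reproduce.** The plan gives no power or effect size for consent-form time. Its 80% power statement (SAP Section 7.b) concerns the incentive-by-risk interaction.

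**Where the forms differ.** Setting the three descriptions in Section 7.a side by side:

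| Element | Consent 1 ($0) | Consents 2 and 3 (paid) |
|---|---|---|
| First-page paragraph | Present; brief no-payment statement | Present; brief payment statement |
| Payment section | No-payment statement | Payment level described |
| Stopping and compensation | Not described | Present (BASC) |
| Risk section | No arm difference described | No arm difference described |

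Only net extra words matter, because Consent 1 is not silent on payment. The two paid forms have the same described elements, so the contrast is mainly $0 versus paid.

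For MOVE IT, the current text supports the payment-level difference only. The change log (II. Changes to Protocol, item 8.a) mentions a first-installment note for the $100 and $300 arms and says that several changes were reflected in updated debriefing and consent forms. It does not establish that this note was printed in the form.

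**Illustration of size.**

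Inputs:
- From the documents: 288 of 576 expected to enroll (Final Protocol Section 6.a). If consent is equal across arms (assumption), that is 288/3 = 96 consenters per arm.
- Assumed: net extra words, reading speed, mean and SD of total time, a two-sided 5% test, no true attention effect, and every added word read in both paid arms.

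*Closed form, linear trend.* Extra seconds = 60 × words / 200, at 200 words per minute. Standardised shift d = seconds / SD. With arm scores −1, 0, 1 and arm means 0, δ, δ, z = d / √(2/96) = d / 0.1443. The rejection rate is Φ(z − 1.96) + Φ(−z − 1.96).

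For scale, the BASC payment scripts in the change log (item 4.a) run to 19 words ($200) or 40 words ($500), plus 13 on withdrawal, so 32 to 53 words gross. They are recruitment and debriefing scripts, not the consent forms.

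| Extra words | Seconds | Rejection, SD 300 s | Rejection, SD 180 s |
|---|---|---|---|
| 32 | 9.6 | 5.6% | 6.6% |
| 53 | 15.9 | 6.6% | 9.4% |
| 150 | 45 | 18% | 41% |

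*Simulation of the Jonckheere-Terpstra test.* Lognormal times, 96 per arm, 1,000 runs per setting, a fixed delay added to both paid arms. Ranges are over coefficients of variation of 0.5 and 1.0. Between 25 and 150 words at 150 to 250 words per minute take 6 to 60 s.

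| Mean total | No delay | 10 s | 20 s | 30 s | 60 s |
|---|---|---|---|---|---|
| 2 min | 4.8–5.5% | 21–32% | 59–79% | 90–98% | 100% |
| 5 min | 4.7–4.9% | 6–9% | 13–22% | 26–40% | 74–90% |
| 10 min | 5.2–6.3% | 6–7% | about 8% | 11–14% | 26–38% |

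The rank test is more sensitive than the linear trend to a fixed delay when times are right-skewed. At SD 300 s and a 20 s delay, the closed form gives 7.5% (z = 0.46). The simulation with mean 5 min and coefficient of variation 1.0, which is the same SD, gives 13%.

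The no-delay column represents a total restricted to identical text. Its 4.7% to 6.3% is consistent with 5%, given a simulation standard error of about 0.7 percentage points.

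**The case against.** The strongest reply is that the plan already contains the main safeguard. Aim II names attention to risk information, the primary attention measure is risk-section time, and understanding has its own quiz. If total time rose only because of payment text, risk-section time would show no matching rise. That stands, and it limits the point to the secondary measure of one secondary outcome.

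The size also rests on forms that cannot be seen. Consent 1 has its own payment wording, and the delay assumes that everyone reads every added word, although a study summarised in Final Protocol Section 12.a reports participants skipping a consent page. The closest wording available gives 5.6% to 9.4% in the closed-form calculation, and the 18% and 41% figures need 150 net extra words. This stands too: no single rejection rate can be put forward as the trial's error rate.

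A reader might go further and drop every section that mentions payment, including the first page. The documents do not support that. The first page describes the study and voluntariness in all arms, and as described it differs only in a brief statement.

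What the reply does not remove is the mismatch itself. The tested total includes sections whose content depends on arm, and the SAP makes no allowance for it.

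**Conclusion.** The point holds for total consent-form time only. Part of any longer total in the paid arms may be added text. The evidence is clearest in BASC, where the paid forms carry the stopping-and-compensation text. It is weaker in MOVE IT, where the current text shows only the payment-level wording. The artefact could be negligible (long form, few net words) or material (short reading times, more words), and the documents do not say which.

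A reader might infer that the attention analysis as a whole, or the test of Aim II, is biased. The documents do not support that: no arm difference in the text of the risk section is described. Enrollment, the three inducement interactions, the stopping rules and the sample size do not use this measure.

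**What to change.** In Final SAP Section 6.b, define the tested secondary attention measure as total time excluding the 'Will I be paid' section and whichever section carries the stopping-and-compensation text. Report whole-form time alongside it. Keep the first-page section in the total unless a check of the three forms shows that its length differs materially by arm. Giving the word count of each section by arm would let readers judge the remaining difference.

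The change is to SAP wording only. Each section is already timestamped, so no new data are needed. The cost is that reading time on any common text in the excluded sections is lost from the tested measure, though it remains in the whole-form figure.
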